### 3. Investigational Plan

#### 3.1. Description of the Study Population

The study will include gout patients not only receiving first-time ULT but will also allow for the inclusion of gout patients who remain hyperuricemic (serum urate  $\geq 6.8$  mg/dl) despite ongoing therapy with uricosurics (e.g. probenecid) or allopurinol at daily doses  $\leq 300$  mg. Uricosurics will require a 14-day wash-out prior to study enrollment. Because febuxostat is non-formulary in the VA and considered only for patients failing or intolerant to allopurinol, patients already taking this agent will be excluded from study participation.

##### Inclusion Criteria:

1. Age  $\geq 18$  years
2. History of gout – crystal proven or historical as defined by ACR criteria listed above
3. Serum urate level  $\geq 6.8$  mg/dl

##### Exclusion Criteria:

1. Stage 4 or 5 Chronic Kidney Disease (CKD) – defined as eGFR of  $<30$  ml/min/1.73 m^2
2. Women younger than 50 years of age
3. Patients with a history of prior solid organ / hematopoietic transplantation
4. Previous allergy or intolerance to allopurinol
5. Patients who are not candidates for any of the recommended prophylactic medications (colchicine, naproxen or glucocorticoids)
6. Patients who in the opinion of the investigator have a high genetic risk for allopurinol hypersensitivity syndrome (AHS\*) unless they have been found to be negative for HLA B5801.
7. Previous history of failure to reach target uric acid levels despite therapy with allopurinol at dose  $> 300$  mg/day
8. Prior febuxostat use
9. Patients with malignancies that are currently active with exception of non-melanoma skin cancer
10. Patients with serum uric acid levels  $>15$  mg/dl
11. Patients with myelodysplasia and hemoglobin of  $< 8.5$  g/dL
12. Patients with chronic liver disease with two or more of the following occurring within the past six months:
  - a. INR  $\geq 1.7$ , not on Warfarin therapy
  - b. Bilirubin  $\geq 2$  mg/dL
  - c. Serum albumin  $<3.5$  g/dL
  - d. Ascites

- e. Encephalopathy
- 13. Current use of azathioprine, mercaptopurine, didanosine, cyclophosphamide, probenecid\*\*, lesinurad or pegloticase\*\*\*
- 14. Enrollment in another randomized interventional clinical trial\*\*\*\*
- 15. Any severe medical condition that, in the enroller's opinion, is likely to compromise the participant's ability to complete the trial (e.g. unable to give informed consent).

\*Please see operational manual for further discussion on genetic risk for AHS.

\*\* Participants on probenecid may be enrolled in the study provided that they undergo a 14-day wash-out period before study entry.

\*\*\* Urate-lowering therapies approved after study kickoff are also excluded.

\*\*\*\* Unless the randomized interventional clinical trial is approved for dual enrollment by VACO

### 3.2. Description of the Intervention Strategy

Eligible patients who consent to participate will be randomized in a 1:1 ratio to receive either allopurinol or febuxostat.

Specified titration of ULT dosing, adhering to the currently recommended initial dosing in gout patients with both normal renal function and CKD stage 3 [1] will be used in Phase 1 (see Table 1 for dose titration schedule).

Specified dose titration will occur until:

- 1) achievement of sUA concentrations at target level < 6.0 mg/dl (5.0 for participants with tophi);
- 2) an adverse event occurs mandating drug discontinuation or dose reduction;
- 3) maximal daily drug dose has been achieved (800 mg/day for allopurinol or 80 mg/day for febuxostat).

During the 24-week 'Maintenance and Optimization Phase' (Phase 2) ongoing dose titration will be allowed if sUA level remains above 6.0 mg/dl, as long as maximal daily drug doses have not been achieved. Dose escalation will not be allowed during the final three study visits of Phase 2 occurring at weeks 36, 42, and 48, to allow for steady-state assessment through week 72 (Phase 3). During Phase 3, participants will be actively followed by monthly phone interviews for flare reporting. In order to reduce the frequency of acute gout flares that may complicate ULT initiation and titration, anti-inflammatory prophylaxis that conforms to recently published guidelines in gout management [2] will be used in Phase 1 and 2.

**Table 1: Phase 1 Dose Titration for weeks 0 to 24 (maximum ULT dose in mg/day by study week)**

	Baseline	3 wks.	6 wks.	9 wks.	12 wks.	15 wks.	18 wks.	21 wks.	24 wks.
Allopurinol	100	200	300	400	500	600	700	800	800
Febuxostat	40	40	40	80	80	80	80	80	80

### **Prophylaxis**

All participants required to be on prophylactic medication for a minimum of 6 months

### **3.3. Definition of Intention to Treat Sample**

All consented and randomized subjects will be accounted for and reported in the CONSORT diagram for the study. By definition, all those randomized subjects will be considered as an intention to treat (ITT) subjects. And all subjects who initiated intervention (i.e., did not drop out or withdraw prior to start of the allocated intervention) will be included in the Data Monitoring Committee (DMC) reports. However, in keeping with clinical practice, only subjects who can tolerate the medications will be considered as our primary analysis subjects. They belong in the phase 3 comparison wherein participants are asked to maintain their level of medication for 24 weeks.

Thus, our primary hypothesis evaluates response during phase 3, while treating phases 1 and 2 as the induction period which identifies those who can tolerate the medications at more than minimum doses. In the secondary analyses we will re-analyze the data using the ITT population to determine if dropout patterns during the induction phases appear to change the results of the comparison. We anticipate that participants who experience severe side effects or who struggle to maintain the medication regimen will drop out during these early phases. Thus, in phase 3 nearly all the remaining patients should find the regimen easy to maintain and have only minor side effects.

Moreover, the ITT analysis that regards any gout flare as a treatment failure is not interpretable. Typically, during titration and stabilization many participants experience flares as the medications reduce sUA level and bring long-term disease under control. These flares are not treatment failures, but instead expected side effects of the titration. Thus, the phase 2 stabilization period is a time buffer that allows us to assert that failures during phase 3 are solely due to treatment (as opposed to titration).

Two analytic sample files consisting of the “ITT” subjects and “Primary Analysis” subjects as defined above will be created and maintained throughout the study. These files will be called the “CSP594\_ITT” file and “CSP594\_PA” file.

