## **5. Statistical Methods**

### **5.1. Handling of Missing Data in Analysis**

During phase 3, 2% of subjects have been estimated to drop out. This is less than the dropout rate in phase 1 and 2 because no one is having dose titration. For purpose of making the power calculation conservative, the rate of attrition has been estimated as being up to 10%, and sample size has been adjusted accordingly to maintain 90% statistical power for the primary analysis.

The high dropout rate reflects clinical practice and not the more vigilant patient monitoring in a clinical trial. Distribution of participants lost to follow-up and missing data on key variables across the treatment groups will be monitored throughout the study. Missing primary endpoint data will not be imputed. All those with missing endpoint data either due to attrition or active withdrawal of consent will be excluded from primary analysis. Missing covariate data will be imputed in selected circumstances as described in [3]. We will explore the possibility of non-random dropout on endpoint data [4].

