### 5.4. Primary Efficacy Analysis

Primary efficacy analysis will include patients who remain on study when phase 3 begins.

The primary outcome is the difference (D) in proportion of patients with one or more gout flares during Phase 3. Seven rheumatologists on our Planning Committee, selected for their expertise in gouty arthritis and clinical trial design, chose  $B = 8\%$ .

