#### 5.4.1. Sensitivity Analysis

- (1) The primary analysis will be repeated on the "per-Protocol" sample with adherence as defined in 3.4 to evaluate efficacy among those adherent to the protocol. We will compare the primary results with the analogous results for the per-protocol participants.
- (2) On the "Primary Analysis" cohort assuming all allopurinol patients with missing primary outcome had at least one gout flare during phase 3 of our study while none of febuxostat patients with missing primary outcome had any gout flare during phase 3 (the worst-case scenario).
- (3) On the "Primary Analysis" cohort assuming all febuxostat patients with missing primary outcome had at least one gout flare during phase 3 of our study while none of allopurinol

patients with missing primary outcome had any gout flare during phase 3 (the best case scenario).

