## 5.5. Secondary Analysis

All secondary analyses are descriptive exploratory analyses and will be done with and without covariate adjustment (age, sex, disease severity, comorbidities, etc.). In some secondary analyses, we will impute values to explicitly explore the effect of missing data.

We describe the proposed analysis for each of the eight secondary objectives:

- 1) To compare the efficacy and tolerability of allopurinol and febuxostat in hyperuricemic participants with gout and stage 3 chronic kidney disease (CKD 3) in reducing gout flares.
  - a. We will carry out the analogues non-inferiority analysis proposed for the primary objective but restricted to participants with stage 3 CKD, using only gout flares observed during Phase 3. Using the full cohort, we will compare gout flare rates of participants with stage 3 CKD to participants with an eGFR  $\geq 60$  mL/min/1.73m^2 with a logistic regression model.
  - b. Tolerability of the two treatments will also be compared in this patient subset and will include comparisons of proportions of adverse events, serious adverse events, and related study withdrawal during the whole study using logistic regression.
  
- 2) To explore the efficacy of the two ULT dosing regimens in achieving the goal of sUA < 6.0 mg/dl evaluated at the end of phase 2. Besides treatment, the primary predictors include the series of sUA measures and dose titrations prior to 48 weeks. This longitudinal analysis will model deviations from the titration protocol.
  - a. The analysis for these longitudinal data will be the mixed effects model with a variance-covariance structure that assumes auto correlated AR(1) sUA measurements over time. We will use PROC MIXED in SAS. At each clinical visit a binary factor will indicate if the titration protocol is or is not maintained. Besides baseline factors such as age, sex, and duration of disease, the model will incorporate time-dependent factors including side effects. Missing data methods will address potential censoring of events among patients who fail to attend clinic visits.
  - b. We will run the same analysis using the biological threshold of sUA < 6.8 mg/dl at the end of phase 2.

- 3) To determine if there are gout flares in phase 3 in participants who achieve a sUA < 6.0 mg/dl by 48 weeks differ compared to those who do not, regardless of treatment assignment.

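### SAP 3.3 puts a tolerance condition on the primary non-inferiority set that SAP 5.4 and the protocol do not have, and the ITT re-analysis it promises is never specified

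*SAP*

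**What the plan says.** SAP 3.3 defines ITT as all randomised subjects and then sets it aside for the primary test: "only subjects who can tolerate the medications will be considered as our primary analysis subjects". It describes Phases 1 and 2 as an induction period that "identifies those who can tolerate the medications at more than minimum doses". The analysis file CSP594_PA is to hold the primary subjects as that section defines them. For the full randomised set, 3.3 says that "we will re-analyze the data using the ITT population" as a secondary analysis.

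SAP 5.4, which governs the test, gives another rule: "Primary efficacy analysis will include patients who remain on study when phase 3 begins". It contains no tolerance condition.

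SAP 5.1 adds: "All those with missing endpoint data either due to attrition or active withdrawal of consent will be excluded from primary analysis". The worst-case and best-case runs in SAP 5.4.1 are confined to the Primary Analysis cohort.

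The protocol calls the trial intent-to-treat (Section VIII, Overview of the Study Design), says the primary analysis follows the ITT principle (Non-adherence), and applies ITT to endpoint data without imputation (Missing Data). Participants with drug hypersensitivity stop study drug but remain in follow-up, and those with other rashes may continue on reduced doses (Section VII, secondary end point 7). Those whose toxicity becomes tolerable can stay on study, and only an explicit decision to leave counts as dropout (Section VIII, Sample Size and Statistical Power Considerations). The same section counts death before a flare in Phase 3 as a failure.

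**The concern.** The SAP offers two rules for the set that decides non-inferiority, and they coincide only if every participant who cannot tolerate the drug leaves before week 48. SAP 3.3 expects that, but the protocol does not require it. A participant who is off drug, or on a minimum dose, and still followed has an observed Phase 3 outcome. That participant is in under 5.4 and can be out under 3.3.

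Tolerance arises after randomisation and may depend on the assigned drug, so removing non-tolerators can move the comparison in either direction. Neither phrase in 3.3 has an operational definition, so the choice of rule could be made after outcomes are known.

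The analysis meant to check this is not specified. The ITT re-analysis appears in neither 5.4.1 nor 5.5, and nothing says how to score someone who left in Phase 1 or 2. The protocol shares that last gap, because its failure rules address Phase 3 only.

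**Working it through.** **Plan's own figure.** Inputs from SAP 4 and 5.4 and Protocol VIII: one-sided alpha 5%, margin 8 points, flare rate 20%, true difference 0, 425 per arm. The chance of declaring non-inferiority is Φ((0.08 − d)/SE − 1.645), with SE unpooled. SE = √(2 × 0.16/425) = 0.02744, so Φ(0.08/0.02744 − 1.645) = 89.8%; the SAP states 90%. At 450 per arm it is 91.2%; the protocol states 91%. The arithmetic is sound, and the issue is who enters the test.

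**3.3 test against 5.4 test.** The documents give no intolerance by arm, so the splits below are assumptions.

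- Participants with Phase 3 outcomes per arm: 475 × 0.90 × 0.98 = 419, using the SAP's 10% attrition and 2% Phase 3 dropout.
- xa and xf are the shares of non-tolerators (allopurinol, febuxostat), q is their flare rate, and febuxostat tolerators flare at 20%.
- The true difference in the 5.4 set is fixed at 8 points, so the 5.4 test errs 5.0% of the time.
- The allopurinol tolerator rate pa solves [(1 − xa)pa + xa·q] − [(1 − xf)0.20 + xf·q] = 0.08. The 3.3 test then sees d = pa − 0.20 with 419(1 − xa) and 419(1 − xf) participants.

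Example with 10% v 5% and q = 45%:

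- Febuxostat overall: 0.95 × 0.20 + 0.05 × 0.45 = 0.2125. Allopurinol overall: 0.2925.
- pa = (0.2925 − 0.045)/0.90 = 0.275, so d = 0.075. SE with 377 v 398 is 0.0305.
- Φ((0.08 − 0.075)/0.0305 − 1.645) = 6.9%.

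| Non-tolerators, allopurinol v febuxostat | Their flare rate | 3.3 test declares non-inferiority |
|---|---|---|
| 10% v 5% | 20% | 2.7% |
| 10% v 5% | 30% | 4.0% |
| 10% v 5% | 45% | 6.9% |
| 6% v 4% | 45% | 5.1% |
| 15% v 5% | 45% | 12.5% |
| 10% v 10% | 45% | 2.7% |
| 5% v 10% | 45% | 1.4% |

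In the last row, with no true difference, power is 74% under 3.3 against 87% under 5.4.

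The 45% is an upper-end assumption. Protocol VIII cites a community cohort, fewer than half of it on urate-lowering therapy, with a 70–75% yearly risk of an attack. At constant hazard, 1 − 0.30^(24/52) = 0.43 and 1 − 0.25^(24/52) = 0.47.

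**Worked case** (hypothetical counts). Tolerators only: 85/377 v 80/398, difference 2.45 points, U = 7.3%, so non-inferior. Add 42 v 21 followed non-tolerators:

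- Flaring at 45%: 104/419 v 89/419, difference 3.58 points, U = 8.4%, so not shown.
- Flaring at 30%: 98/419 v 86/419, U = 7.6%, so the conclusion does not change.

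**Death rule.** If two deaths fall in one arm of 450, (0.20 × 448 + 2)/450 − 0.20 = 0.4 points.

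**The case against.** The strongest reply is that 3.3 explains rather than restricts. It says those with severe side effects are expected to drop out early, so nearly everyone left should find the regimen easy to maintain. The SAP has no tolerance variable or dose cut-off, adherence is handled separately through the per-protocol sample, and 5.4 carries no filter. This reading is plausible and may be the intended one. It does not settle the matter, because 3.3 uses the word only, refers to more than minimum doses, and ties the analysis file to its own definition.

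A reader might infer that the SAP is certain to exclude non-tolerators, or that it favours allopurinol. The documents support neither. Protocol III reports withdrawals for rash generally well below 5% and similar across groups, and puts allopurinol hypersensitivity at up to 1%. Protocol IV says that better tolerability of febuxostat has never been reported in head-to-head trials, and Protocol XII calls rash frequency similar. Those trials used lower allopurinol doses, so this does not rule out an imbalance, but it gives no ground for presuming one. Participants whose toxicity was made tolerable would leave the 3.3 set only if the minimum-dose phrase were enforced, and non-adherence is not intolerance.

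The scenarios are also generous. They take off the conservative 10% attrition and then assume a further group of non-tolerators among those who remain.

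A reader might also cite the protocol's statements that everyone is followed and analysed in Phase 3. Those concern reaching the urate goal, not tolerance. The conflict rests on the ITT statements, and the protocol's own ITT plans on 900 retained of 950, which is close to 5.4.

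Finally, the SAP has some general cover: "We will explore the possibility of non-random dropout on endpoint data" in 5.1 and "In some secondary analyses, we will impute values to explicitly explore the effect of missing data" in 5.5. The protocol adds a confirmatory survival analysis and says secondary analyses treat dropout as the primary one does. None of these gives an outcome rule for Phase 1–2 leavers.

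**Conclusion.** SAP 3.3 is wrong as written and should be fixed. Read literally, it conflicts with SAP 5.4 and with the protocol's ITT primary analysis, and it would remove randomised participants with observed outcomes from the confirmatory test. SAP 5.1 also leaves out the protocol's rule for deaths in Phase 3, which is a small matter in size.

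The direction of any bias cannot be known from the documents. Across the assumed splits the false-claim rate runs from 1.4% to 12.5% against 5.0%. It rises materially only when allopurinol non-tolerators are clearly in excess and also flare at about 45%. The grounds for the change are the contradiction and the unspecified check, not a demonstrated bias, so this is a should-fix and not a fatal flaw.

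**What to change.** 1. Delete the tolerance condition from 3.3 and use the 5.4 set, analysed as randomised. Count Phase 3 flares for everyone with Phase 3 follow-up, active or passive, whatever their drug status or dose.
2. Carry the protocol's rule for death before a flare in Phase 3 into 5.1.
3. Report any tolerator cohort as supportive only, beside per-protocol.
4. List the ITT re-analysis in 5.4.1 with its rule: all randomised by assigned arm, observed Phase 3 flares where available, and outcomes missing through Phase 1–2 or Phase 3 loss multiply imputed by arm. Then raise the imputed allopurinol flare rate until the upper limit crosses 8% (tipping point). The existing run "assuming all allopurinol patients with missing primary outcome had at least one gout flare during phase 3" can stay, but it covers only the Primary Analysis cohort.

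As an illustration of the tipping point, take 475 per arm, 10% missing in each, observed rates of 22% v 20%, and missing febuxostat at 20%. With a single-imputation SE, the limit is crossed when missing allopurinol participants flare at 38%.

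The cost is SAP wording plus analyses on the planned CSP594_ITT and CSP594_PA files. At an equal 10% non-tolerator share flaring at 45%, power is 87.0% under 5.4 and 86.5% under 3.3. The upper limit may be less favourable, and off-drug participants can dilute an on-drug difference: with 10% of each arm off drug and flaring alike, 8 points becomes 0.90 × 8 = 7.2. Per-protocol results must therefore stay beside the primary result.

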### **3.4. Definition of per-Protocol sample**

Participant adherence to protocol-directed study treatment will be assessed via dosage review and participant interview. We will use the question and pill count data to determine if a participant took 80% or more of treatment medication. The per-protocol population will be defined as participants remaining on the same treatment in phase 3 of the study with 80% adherence.

We will compare the primary results with the analogous results for the per-protocol participants.

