The test of the primary hypothesis compares the treatments without adjustment for any covariates. The secondary analyses, particularly secondary analysis will confirm or not confirm the primary hypothesis by considering variations on the primary analysis including logistic regression models that adjust for covariates. We note that logistic regression analysis yields a treatment odds ratio rather than the difference between proportions. In this case, to carry out the non-inferiority test, we will estimate the difference between treatments by linking the odds ratio to the overall proportion of participants who have one or more gout flares.

In addition to testing the primary hypothesis, extensive descriptive analyses outlined in (BRDP) will compare treatments with respect to selected variables among the demographic, medical history, laboratory values, anthropomorphic, vital sign, quality-of-life, alternative outcome, and side effect variables. Simple unadjusted comparisons will apply Student's t-test to continuous variables, the Wilcoxon test to highly skewed continuous or ordinal variables and will apply the Chi-square test (or Fisher's exact test) to categorical variables.

Non-adherence

Of relevance to this study, observational studies have indicated relatively poor adherence in patients with gout (40, 87-90) However, Dalbeth et al. (91) found that higher doses of allopurinol were associated with sUA levels at target independent of adherence with treatment. Because all study participants will receive active therapies of proven efficacy for lowering sUA levels as well as prophylactic treatment of acute gout symptoms, compliance issues are expected to be minimal in this trial. Other studies in rheumatoid arthritis have shown that if patients are doing well, issues of poor treatment adherence are minimized (92).

Participant adherence to protocol-directed study treatment will be assessed via pill counts, prescription renewals, and participant interview. We will use the question and pill count data to determine if a participant took 80% or more of treatment medication. The per-protocol population will be defined as participants remaining on the same treatment throughout the entirety of the study with 80% adherence.

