**Table A5. Protocol Deviations**

Description of Protocol Deviation	Sample (N= )	Form Location	Element Codes
Informed consent and/or HIPAA authorization not signed until after study procedures started	N (%)	PD	DVDECOD=1
Eligibility criteria violated	N (%)	PD	DVDECOD=2
Allopurinol/Febuxostat not prescribed and/or not dispensed as per protocol	N (%)	PD	DVDECOD=3
Required study procedure not completed	N (%)	PD	DVDECOD=4
SAE not reported per protocol	N (%)	PD	DVDECOD=5
Lab blood draws not obtained as per protocol	N (%)	PD	DVDECOD=6
Participant took Probenecid and or/ Lesinurad	N (%)	PD	DVDECOD=7
Participant took other excluded medication after randomization	N (%)	PD	DVDECOD=8
Required source documentation could not be obtained	N (%)	PD	DVDECOD=9
Patient seen outside visit window (Study visits will have a window +/- 1 week in Phase 1 and +/- 2 weeks in Phase 2 and 3)	N (%)	PD	DVDECOD=10
Other protocol deviation 	N (%)	PD	DVDECOD=11

See Appendix B.

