**Table B7. Study Medication Adherence**

Adherence	Baseline (n= )	Form Location
Phase 1		
<80%	N (%)	Study Medication Adherence
>= 80%	N (%)	Study Medication Adherence
Phase 2		
<80%	N (%)	Study Medication Adherence
>= 80%	N (%)	Study Medication Adherence
Phase 3		
<80%	N (%)	Study Medication Adherence
>= 80%	N (%)	Study Medication Adherence
Overall		
<80%	N (%)	Study Medication Adherence
>= 80%	N (%)	Study Medication Adherence

Adherence is computed as (Total capsules/Tablets taken/Total capsules/tablets given) \* 100

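### The per-protocol set is defined by same treatment and 80% adherence only, so it can retain participants given the wrong drug or dose, or who added another urate-lowering drug

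*SAP*

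**What the plan says.** SAP 3.4 sets two conditions: "The per-protocol population will be defined as participants remaining on the same treatment in phase 3 of the study with 80% adherence". The 80% is judged as follows: "We will use the question and pill count data to determine if a participant took 80% or more of treatment medication". SAP 3.4 also names dosage review as a way of assessing adherence, but does not say how it enters the 80% rule. The one formula given is in the footnote to SAP Table B7: "Adherence is computed as (Total capsules/Tablets taken/Total capsules/tablets given"), multiplied by 100.

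The protocol (Section VIII, Non-adherence) uses the same two conditions over a different period: "The per-protocol population will be defined as participants remaining on the same treatment throughout the entirety of the study with 80% adherence".

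SAP 5.4.1(1) repeats the primary non-inferiority analysis on this "sample with adherence as defined in 3.4 to evaluate efficacy among those adherent to the protocol". The protocol (Section VIII, secondary objective 8) repeats all major analyses on it.

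SAP Table A5 records deviations by code. Four matter here:
- Code 2: eligibility violation.
- Code 3: "Allopurinol/Febuxostat not prescribed and/or not dispensed as per protocol".
- Code 7: "Participant took Probenecid and or/ Lesinurad".
- Code 8: other excluded medication after randomisation.

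These codes appear in the shells for the data monitoring committee. Neither document ties them to the per-protocol set.

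**The concern.** The label and the filter do not match. SAP 5.4.1 speaks of adherence to the protocol, while SAP 3.4 tests only whether the participant stayed on treatment and took most of what was handed out. The protocol (Section XVIII, Protocol deviations) says that a participant's missed doses are not a deviation, but that incorrectly administered or prescribed study drug is. The per-protocol set thus filters on the first and ignores the second.

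This matters because the trial tests non-inferiority. If some participants in each arm receive the other drug, or add a further urate-lowering drug, the difference in flare proportions can shrink towards zero, and that favours the conclusion the trial hopes to reach. A per-protocol analysis that keeps these participants carries the same dilution as the primary analysis, so agreement between the two says less than it seems to.

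**Working it through.** **1. Which participants pass the two conditions**

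| Situation | Same treatment in Phase 3? | 80% adherence? | Other rule that removes them |
|---|---|---|---|
| Switched to the other drug during Phase 3 | Arguably not | Possibly | None needed |
| Given the wrong drug consistently | Can pass | Yes, if taken | None |
| Given a materially wrong dose | Yes | Yes, if taken | None |
| Added probenecid or lesinurad | Yes | Yes | Early termination, for regular need only (SAP Table A6) |
| Eligibility violation | Yes | Yes | None |

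The Table B7 ratio divides by units given, so it cannot show that the wrong units were given.

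**2. Whether another planned analysis covers this**

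- SAP 5.4.1(2) and (3) vary only missing outcomes.
- The ITT re-analysis in SAP 3.3 addresses dropout in Phases 1 and 2 and keeps every participant with a deviation.
- SAP 5.5(2) models departures from titration, but for serum urate. SAP 5.5(8) lists titration levels as a covariate for the primary result. Neither repeats the non-inferiority test without the deviating participants.

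**3. The plan's own power figures**

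Inputs: margin B = 8%, one-sided 5%, true difference 0, flare rate 20% (range 15 to 25%), 450 per arm (protocol Section VIII) or 425 per arm (SAP 4).

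Power = Φ(B / √(2p(1−p)/n) − 1.645)

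- p = 20%, n = 450: standard error 0.02667; Φ(3.000 − 1.645) = 91.2%.
- p = 15% and 25%, n = 450: 95.7% and 87.0%.
- p = 20%, n = 425: standard error 0.02744; Φ(2.915 − 1.645) = 89.8%.

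These match the stated 91%, 96%, 87% and 90%. Nothing below rests on an error in them.

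**4. Dilution if deviating participants are kept**

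Assume that a share f of the per-protocol set, equal in both arms, has a deviation. The documents give no value for f.

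- Deviating participants show no drug difference: D = 8% × (1 − f). This gives 7.6% at f = 5% and 7.2% at f = 10%.
- Deviating participants took the other arm's drug: D = 8% × (1 − 2f). This gives 7.2% and 6.4%.

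The chance of wrongly finding non-inferiority in this check, with 425 per arm and febuxostat held at 20%, is Φ((8% − D)/SE − 1.645), where SE = √([0.2×0.8 + (0.2+D)(0.8−D)]/425). At D = 7.2%, SE = 0.02902 and Φ(0.276 − 1.645) = 8.5%.

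| f | No drug difference | Other arm's drug |
|---|---|---|
| 0% | 5.0% | 5.0% |
| 2% | 5.6% | 6.2% |
| 5% | 6.6% | 8.5% |
| 10% | 8.5% | 13.8% |
| 20% | 13.8% | 30.0% |

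**5. Cost of removing them**

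With n = 425(1 − f) and a true difference of 0, power in this check falls from 89.8% to 89.3% (f = 2%), 88.4% (5%), 86.9% (10%) and 83.2% (20%).

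**The case against.** The strongest reply is that the plan gives the set a narrower purpose. Protocol Section VIII (secondary objective 8) says that repeating analyses on the per-protocol population should either confirm the results or show that adherence changes them. For that question the two conditions fit. This stands in part: a reader might infer that the set was designed to detect contamination, and the documents do not say so. Confirming a non-inferiority result is nevertheless one of its stated uses, and no other planned analysis fills the gap.

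A reader might also infer that all these deviations favour non-inferiority. The documents do not support that:
- Eligibility violations can act either way. The exclusion criteria include prior allopurinol intolerance and failure above 300 mg/day. Enrolling such patients would plausibly count against allopurinol.
- Several excluded drugs that code 8 could capture (azathioprine, mercaptopurine, didanosine, cyclophosphamide) are not presented as urate-lowering.
- Regular need for an excluded drug is a listed reason for early termination, so some users will leave the study.

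Two objections to a blanket exclusion also stand. Code 3 carries no grade or timing, so an early prescribing slip could remove someone from a comparison at weeks 49 to 72. And a urate-lowering drug may be added because control is poor; if that happens more often on allopurinol, excluding those participants flatters allopurinol. Blinded review does not prevent this selection.

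**Conclusion.** The concern holds in a limited form. Neither document removes from the per-protocol set a participant who took the wrong study drug or a materially wrong dose throughout, or who added another urate-lowering drug and stayed on study. These deviations can weaken the per-protocol check on non-inferiority.

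The size is unknown. It rests on an assumed deviation share, equal in both arms, with no drug difference (or a reversed one) among those affected. On those assumptions the effect is slight at 2% and material at 10% or more.

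It would be wrong to infer that the primary conclusion is compromised. The decision rule in SAP 5.4 uses a different analysis set and does not depend on this one. This is a low-priority improvement to one sensitivity analysis.

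**What to change.** In SAP 3.4, keep the two existing conditions and also exclude:
- (a) code 3 deviations that blinded review finds changed the drug received, or materially changed the dose received relative to the protocol, going into or during Phase 3;
- (b) code 7, and code 8 where the drug is urate-lowering, when use overlaps Phase 3 or could affect it;
- (c) code 2 violations that blinded review judges relevant to the flare outcome or to treatment response.

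Fix the list blind to arm before database lock and tabulate exclusions by arm and code. Report this analysis beside the adherence-only per-protocol set, so that any selection produced by the exclusions is visible. The different adherence periods in SAP 3.4 and the protocol are a separate matter, but should be reconciled in the same edit.

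The cost is a short addition to SAP 3.4 and a blinded review of codes already collected. The downsides are a smaller per-protocol set and possible selection, both confined to a sensitivity analysis.
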